4.7.3.2 Derivation or calculation of outcome variables

All individual values and changes to baseline will be listed and summarized descriptively.

Abnormal findings for vital signs and ECGs should only be reported as AEs if they are accompanied by clinical symptoms, constitute SAEs or lead to discontinuation of treatment with the investigational product.

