Visit 4: End of Treatment (Days 14 & 15 ±1 day): Patients will attend the CPU with their BronkoTest[®] diary card and study medication on the morning of Day 14 in fasted state, having fasted from midnight (water will be allowed for thirst up until 1 hour before dosing) and having withheld taking their morning dose of study medication, and stay until the morning of Day 15. Blood will also be collected pre-dose for assessment of PK, hsCRP and serum amyloid A. Before administration of the morning dose on Day 14, safety assessments (vital signs, ECG, lung function, haematology, clinical chemistry, urinalysis and urine drug screen) will be performed. Patients will then take their morning dose of study medication in the CPU. This will be the final dose of study medication. At 1 hour post-dose, an ECG will be recorded. Approximately 1-2 hours after this last dose, patients will provide an induced sputum sample (around the same time they had the induced sample on Day -1); weight of the sample will be recorded, and the sample processed for neutrophils and AZD9668 levels.

All urine produced over the 24 hours after the last dose will be collected for measurement of desmosine levels and AZD9668 concentrations. Urine will be collected for time periods 0-4 hours, 4-12 hours and 12-24 hours. Aliquots from each of these collections will be taken for urine PK, and an aliquot from the pooled sample will be taken for urine desmosine. Serial blood samples will be collected for PK analysis at pre-dose and at 0.25, 0.5, 1, 2, 3, 4, 5, 6, 8, 12, and 24 hours post dose. On the morning of Day 15, a spontaneous sputum sample will be collected for quantitative bacteriology, and the patients will be discharged from the CPU with their BronkoTest[®] diary card to bring to their follow-up visit.

Visit 5: Follow-up (Day 21 ±3 days): Patients will return to the CPU with their BronkoTest[®] diary card in fasted state, having fasted from midnight (water allowed), for follow-up safety assessments (physical examination, vital signs, ECG, lung function, haematology, clinical

chemistry and urinalysis). A blood sample for hsCRP and serum amyloid A will also be collected at this visit.

Throughout the study, lung function measurements should be performed at the same time of day ± 2 hours in relation to the time point at Visit 1 (baseline).

Each patient will attend the visits as outlined in Figure 1.

[figure not shown]

Table 1Study plan

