4.7.1 Adverse events

4.7.1.1 Definitions

The definitions of adverse events (AEs), serious adverse events (SAEs) and other significant adverse events (OAEs) are given below. It is of the utmost importance that all staff involved in the study are familiar with the content of this section. The principal investigator is responsible for ensuring this.

Adverse event

An adverse event is the development of an undesirable medical condition or the deterioration of a pre-existing medical condition following or during exposure to a pharmaceutical product, whether or not considered causally related to the product. An undesirable medical condition can be symptoms (eg, nausea, chest pain), signs (eg, tachycardia, enlarged liver) or the abnormal results of an investigation (eg, laboratory findings, electrocardiogram). In clinical studies, an AE can include an undesirable medical condition occurring at any time, including run-in or washout periods, even if no study treatment has been administered.

Serious adverse event

A serious adverse event is an AE occurring during any study phase (ie, run-in, treatment, washout, follow-up), and at any dose of the investigational product, comparator or placebo, that fulfils one or more of the following criteria:

- Results in death
- Is immediately life-threatening
- Requires in-patient hospitalisation or prolongation of existing hospitalisation
- Results in persistent or significant disability or incapacity
- Is a congenital abnormality or birth defect

• Is an important medical event that may jeopardise the patient or may require medical intervention to prevent one of the outcomes listed above.

The causality of SAEs (ie, their relationship to study treatment) will be assessed by the investigator(s), who in completing the relevant case report form must answer "yes" or "no" to the question "Do you consider that there is a reasonable possibility that the event may have been caused by any of the following – study medication – other medication?" For further guidance on the definition of a SAE and a guide to the interpretation of the causality question, see Appendix B to the Clinical Study Protocol.

Note that SAEs that could be associated with any study procedure should also be reported. For such events the causal relationship is implied as "yes".

Other Significant Adverse Events (OAE)

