AEs and any abnormalities in laboratory tests, vital signs or physical examination of clinical relevance will be followed up until resolution or no further improvement is expected in the opinion of the Investigator. Patients who drop out during the study for reasons other than discontinuation of study drug will be followed up for the planned duration of the study. Abnormalities in laboratory tests and vital signs will be recorded and reported on the laboratory reports and CRFs respectively. Abnormalities in these variables will be identified, analysed and reported in the Clinical Study Report. Laboratory results that constitute a SAE or lead to discontinuation of the study drug will be recorded and reported as an AE. In addition, any abnormality in laboratory tests which meets the stopping criteria as described in Section 3.3.5, will be recorded as an AE.

Should an overdose (accidental or deliberate) occur, it must be reported in accordance with the procedures described in Section 9.3, Procedures in case of overdose, regardless of whether the overdose was associated with any symptom or not. All symptoms associated with the overdose should be reported as AEs.

Should a pregnancy occur, it must be reported in accordance with the procedures described in Section 9.4 - Procedures in case of pregnancy. Pregnancy in itself is not regarded as an AE unless there is a suspicion that an investigational product may have interfered with the effectiveness of a contraceptive medication.

If patients annotate their diary card or questionnaires with comments, these will be reviewed by the study centre staff in consultation with the patient, in case the annotation represents an AE.

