- Evidence of haemolysis as evidenced by the following:
 - Reticulocyte count of over 5%, and

At least two of the following:

- a drop in haemoglobin below 10.5 g/dl
- decrease of 25% in haptoglobin. (The value post-dose to be compared with the average of two pre-dose values. The value should also be 15% below LLN).
- increase of 25% in unconjugated bilirubin or lactate dehydrogenase (LDH).
 (The value post-dose to be compared with the average of two pre-dose values. The value should also be 15% above ULN)
- A platelet count of below $80 \ge 10^9$ /L confirmed by a repeat test (in the absence of obvious platelet clumping in a peripheral blood film).
- A QTcF >500 ms on active treatment (QT interval corrected for heart rate by Fridericia method) or a QTcF prolongation >60 ms on average compared to baseline, confirmed by a repeat ECG in 30 minutes.

Section of protocol affected:

3.3.5, Discontinuation of patients from treatment or assessment3.3.5.1, Criteria for discontinuation, Stopping criteria for the whole study, page 30

Previous text:

Stopping criteria for the whole study

- Two or more patients on active treatment are discontinued because of either an ALT/AST level ≥3 x ULN or any pattern of LFT abnormalities giving cause for concern
- Two or more patients on active treatment are discontinued because of evidence of haemolysis
- Two or more patients on active treatment are discontinued because of a platelet count of below $80 \times 10^9/L$

Revised text:

Stopping criteria for the whole study

- Two or more patients on active treatment are discontinued because of either an ALT/AST level ≥3 x ULN or any pattern of LFT abnormalities giving cause for concern
- Two or more patients on active treatment are discontinued because of evidence of haemolysis
- Two or more patients on active treatment are discontinued because of a platelet count of below $80 \ge 10^9/L$
- A QTcF >500 ms on active treatment (QT interval corrected for heart rate by Fridericia method) or a QTcF prolongation >60 ms on average compared to baseline, confirmed by a repeat ECG in 30 minutes in 2 or more subjects on active treatment

Section of protocol affected:

Section 10, References, page 58

Added reference:

GOLD 2007

Global Initiative for Chronic Obstructive Lung Disease. Global Strategy for the Diagnosis, Management, and Prevention of Chronic Obstructive Pulmonary Disease. Updated 2007. http://www.goldcopd.org

Reason for Amendment:

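### The rule that records stopping-criterion hits as adverse events covers laboratory tests only, so an asymptomatic QTcF hit may be left out of the AE count unless it is judged an SAE

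*Protocol*

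**What the plan says.** Four parts of the protocol decide whether an ECG finding becomes an adverse event.

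- **Section 4.7.1.1 (general definition).** An undesirable medical condition can be "the abnormal results of an investigation (eg, laboratory findings, electrocardiogram". No symptoms are required.
- **Section 4.7.3.2 (vital signs and ECG).** This is narrower: "Abnormal findings for vital signs and ECGs should only be reported as AEs if they are accompanied by clinical symptoms, constitute SAEs". The only other route it allows is a finding that causes study treatment to be stopped.
- **Section 4.7.1.2 (recording).** It provides that "any abnormality in laboratory tests which meets the stopping criteria as described in Section 3.3.5, will be recorded as an AE". ECG is not mentioned.
- **Amendment 01, revised Section 3.3.5.1.** It adds to the individual criteria "A QTcF >500 ms on active treatment (QT interval corrected for heart rate by Fridericia method", or a mean prolongation above 60 ms from baseline, confirmed by a repeat ECG. The same condition in two or more subjects on active treatment becomes a whole-study criterion. The changes in the available text concern Sections 3.3.2, 3.3.3, 3.3.5.1 and 10, not Section 4.7.

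On laboratory findings, Section 4.7.2.3 sets the same three conditions as 4.7.3.2 and makes no exception for stopping criteria.

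On timing, Section 3.1 states that the Day 14 morning dose is the last one, and then: "At 1 hour post-dose, an ECG will be recorded". Under Section 4.7.1.2, AEs are recorded until Visit 5.

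**The concern.** Before the amendment every measured stopping criterion was a laboratory one (ALT/AST, haemolysis, platelets), so the sentence in 4.7.1.2 covered them all. Adding QTcF left one measured criterion whose hit is not automatically an AE.

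Adverse events are a primary tolerability outcome, and QT prolongation is a cardiac risk that Section 3.2.2 itself raises from the dog telemetry data. If sites follow 4.7.3.2 as written, the AE table could omit a silent QTcF hit and yet include an equally silent platelet hit. This is a collection rule. A statistical analysis plan cannot restore AEs that sites were told not to record.

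**Working it through.** No figure in the plan is at issue. The check is a comparison of rules, followed by one proportion.

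**1. The rules side by side.** Take a finding that meets a Section 3.3.5 criterion, has no symptoms, is not judged serious, and does not lead to treatment being stopped.

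| Finding | 4.7.1.1 | 4.7.1.2 | Specific section |
|---|---|---|---|
| Laboratory | can be an AE | is an AE | not an AE (4.7.2.3) |
| QTcF | can be an AE | not covered | not an AE (4.7.3.2) |

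The laboratory row contains a conflict between 4.7.1.2 and 4.7.2.3. In the QTcF row nothing requires recording, and the specific rule excludes it.

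**2. When the discontinuation route fails.** There are two situations.

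- *During dosing.* Section 3.3.5.1 words its criteria as possible reasons for discontinuation. A hit that does not lead to discontinuation falls outside the AE rule.
- *After the last dose.* No treatment remains to be stopped, so this condition cannot be met.

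**3. Which ECG matters most.** From Section 3.1 and Table 1, footnote b:

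- Day 1: 1 hour after the first dose, so single-dose exposure.
- Day 2: before the morning dose. Day 3: before discharge, at no fixed interval from that morning's dose.
- Days 7 and 14: before the morning dose, so at trough.
- Day 14: a further ECG 1 hour after the final dose.
- Visit 5: Day 21, nominally 7 days after the last dose.

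Section 3.2.1 gives a median steady-state tmax of 1 hour at every dose in healthy volunteers. The Day 14 ECG at 1 hour is therefore the only one scheduled at a fixed time near peak at steady state. Section 3.2.1 also says that fasting is imposed so that ECGs can be taken when Cmax is at its highest.

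Visit 5 adds little. The longest geometric mean half-life in Section 3.2.1 is 14.99 h, and 7 × 24 / 14.99 = 168 / 14.99 = 11.2 half-lives.

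**4. Weight of one case.** Active patients: 18 × 2/3 = 12, which agrees with the 12 stated in Section 3.2.1.

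- One case recorded: 1/12 = 8.3% (exact 95% CI 0.2% to 38.5%).
- The same case not recorded: 0/12 = 0% (exact two-sided 95% upper limit 26.5%).

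**5. Is the hit visible elsewhere?** ECG is a primary tolerability variable in its own right, and 4.7.3.2 says individual values and changes from baseline will be listed and summarised. However, 4.7.3.1 says only the overall evaluation is captured, with the original ECGs kept in the medical record, and 6.4.4 names only the overall evaluation for analysis. Section 4.7.1.2 promises reporting of laboratory and vital-sign abnormalities in the study report without naming ECG.

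**The case against.** **The definitions can be read together.** Section 4.7.1.1 says only that an abnormal result can be an AE, and 4.7.3.2 may be the specific rule that narrows it. This is a fair reading. It weakens any claim of outright contradiction between those two sections, but it leaves the gap in place, because the narrower rule is the one that leaves the hit out.

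**The SAE route stays open.** A reader might infer that such a hit can never reach the AE count. The documents do not support that: 4.7.1.1 lets an important medical event be judged serious without symptoms. Recording then depends on judgement, whereas 4.7.1.2 makes a laboratory hit automatic.

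**The data are not lost.** ECG is analysed separately, and 4.7.3.1 sends abnormalities, including QTc values, for qualified review. This stands in part. The references to overall evaluation make it uncertain that a QTcF hit would appear as a distinct event in the report.

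**The laboratory comparison is not clean.** Section 4.7.2.3 would exclude a silent laboratory hit that 4.7.1.2 includes. This is correct, and it widens the repair to that section.

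**Stopping the study does not depend on AE coding.** Also correct. The whole-study QTcF criterion counts subjects with hits directly, so the gap gives no reason to think that rule would fail.

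**The study is small and descriptive.** It tests no hypotheses and compares arms informally. That limits the consequence to how the AE table reads.

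**Conclusion.** The point holds as an inconsistency in AE recording. After Amendment 01, an asymptomatic QTcF hit that does not lead to discontinuation may be left out of the AE count unless it is judged an SAE. The exposure is greatest at the Day 14 ECG 1 hour after the final dose. One uncounted case is 8.3% of the 12 active patients.

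This assumes that sites follow 4.7.3.2 over the general definition, that all 12 active patients are dosed and assessed, and that the unavailable remainder of Amendment 01 does not change Section 4.7.

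Two wider readings are tempting but not supported:

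- *Every ECG after the last dose is equally affected.* Visit 5 is nominally a week off drug, and the 500 ms limb is worded for patients on active treatment, so Day 14 at 1 hour carries the weight.
- *Vital signs classed as abnormal and clinically significant should also be AEs.* Nothing in 4.7.3.1 requires that, vital signs are not among the measured stopping criteria, and 4.7.1.2 already provides for reporting vital-sign abnormalities in the study report.

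**What to change.** Four wording changes, all to AE recording:

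1. In 4.7.1.2, extend the stopping-criterion sentence to cover *laboratory tests or ECG (including QTcF), whether or not treatment is still ongoing*.
2. In 4.7.3.2, add the matching exception for ECG findings that meet a Section 3.3.5 criterion.
3. In 4.7.2.3, add the same exception for laboratory findings, so that it agrees with 4.7.1.2.
4. In 4.7.1.1, cross-refer to the recording rule.

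The cost is about one sentence per section and an instruction on the AE page. A few more AEs may be recorded. No measurement is added, and the stopping criteria themselves are not changed.

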4.7.4 Other safety measurements and variables

Lung function tests will be recorded whilst the subject is in a sitting position at the time points specified in the study flow chart (Table 1).

The lung function tests will comprise:

- Forced expiratory volume in one second (FEV₁)
- Forced vital capacity (FVC)
- Slow vital capacity (SVC)
- Inspiratory capacity (IC)

Spirometry will be performed with the same mobile bi-directional digital computerised spirometer (Masterscope[®], Jaeger, Höchberg, Germany) with software Labman, version 4.53, for each subject throughout the study according to the European Respiratory Standards (ERS).

All lung function tests will be repeated, until three technically acceptable measurements have been made and the maximum of these three measures will be recorded in the CRF. Post-bronchodilator values will be obtained 20 minutes after inhalation of 400μ g of salbutamol. The details of the procedure for the performance of the laboratory tests will be given in the laboratory handbook.

4.8 Volume of blood sampling and handling of biological samples

The total volume of blood that will be drawn from each patient in this study is as follows:

Table 3	Volume of blood to be	drawn from each patient

			-	
Assessment		Sample volume (mL)	No. of samples	Total volume (mL)
TNFα desmosine	e and IL-8 (plasma)	10.0 mL	3	30.0
Amyloid-A and hs-CRP (serum) PK		2.7 mL	4	10.8
		3.0 mL	25	75.0
Virology		2.6 mL	1	2.6
Pregnancy/FSH		2.7 mL	1	2.7
Safety	Clinical chemistry	7.5 mL	6	45.0
	Haematology	2.7 mL	6	16.2
Genotyping		9.0 mL	1	9.0

Table 3	Volume of blood to be drawn from each patient
---------	---

Assessment	Sample volume (mL)	No. of samples	Total volume (mL)
Total			191.3

4.8.1 Analysis of biological samples

4.8.1.1 Clinical chemistry samples

The analyte stability limits defined by will be applied to all analyses performed on behalf of AstraZeneca. Will not analyse samples that fall outside these stability limits. Analytical data will not be reported if found to have been derived from a sample that fell outside these stability limits. The standards of procedure followed by will inform a sample that for a scordance with its Standard Operating Procedures. Will inform AstraZeneca of the stability limits relevant to this study before the first patient gives informed consent to take part in the study.

If **the second s**

4.8.1.2 Pharmacokinetic samples

The long-term stability of the analyte in plasma and urine has been documented in method validation produced by **and the stability in the stability has been demonstrated**. Results from analyses of samples stored longer than the time period for which stability has been demonstrated should not be reported unless complementary analyte stability data is acquired and amended to the relevant method validation report. Documentation of the time period for which stability has been demonstrated is available at **an analyte stability**.

4.9 Genetic measurements and co-variables

4.9.1 Collection of samples for genetic research

Patients will provide a blood sample as per the inclusion criteria and visit schedule.

A single venous blood sample 9 mL will be collected into a polypropylene tube containing ethylenediamine tetra-acetic acid (EDTA) and gently inverted a minimum of 5 times to mix thoroughly. Tubes will be labelled with the protocol study number, centre number, enrolment code and/or randomisation number and date of sample collection. No personal identifiers (patient name, initials or date of birth) will be placed on the tube or accompanying documentation. A record of the date of the patient consent to the genetic research and the date of the blood sample collection will be recorded in the appropriate section of

Genotype is a stable parameter; therefore if for any reason the blood sample is not drawn at Visit 2, it may be taken at any visit until the last study visit. The genetic blood sample should ideally be drawn through the same cannula used to draw blood samples required for the main study.

4.9.1.1 Sample processing and shipping

Samples will be frozen (-20°C or below) and transported to the relevant DNA extraction laboratory within one month of collection and must remain frozen at all times.

Where possible samples should be shipped in batches and shipment should be coordinated with the receiving site to ensure that samples arrive within working hours. A requisition sheet, detailing the protocol study number, centre number, enrolment code and/or randomisation code and date of sample collection, should accompany the shipment.

4.9.1.2 Storage and coding of DNA samples

The processes adopted for the coding and storage of samples for genetic analysis are important to maintain patient confidentiality.

For all samples irrespective of the type of coding used the DNA will be extracted from the blood sample. The DNA sample will be assigned a unique number replacing the information on the sample tube. Thereafter, the DNA sample will be identifiable by the unique DNA number only. The DNA number will used to identify the sample and corresponding data at the AstraZeneca genetics laboratories, or at the designated contract laboratory. No personal details identifying the individual will be available to any AstraZeneca employee working with the DNA.

'The blood samples and data for genetic analysis in this study will be coded. Each blood sample will be labelled with the study number and subject number. Only the investigator will be able to link the blood sample to the individual subject. The sample and data will not be labelled with a personal identifier. The link between the subject enrolment/randomisation code and the DNA number will be maintained

All DNA samples will be stored under secure conditions with restricted access at AstraZeneca. The blood, DNA samples or data derived from the samples may be made available to groups or organisations working with AstraZeneca on this study or as part of the development drug project. However, the samples and any results will remain the property of AstraZeneca at all times. AstraZeneca will not give blood, DNA samples or data derived from the samples to any other parties, except as required by law.

4.9.1.3 Summary of genetic assessments and analysis

The purpose of the genetic research is to generate data for use in future retrospective analyses. Future analyses will explore genetic factors that may influence the disposition, efficacy, safety and tolerability to AZD9668 and/or susceptibility to or prognosis of COPD under investigation in this protocol. The results of the genetic research will not form part of the

clinical study report for this study. The results may be pooled with genetic data from other studies on AZD9668 to generate hypotheses to be tested in future studies.

